## Appendix H: Criteria for Response assessment in Acute Lymphoblastic Leukemia (based on NCCN Guidelines Version 1.2013)

Response classification in ALL for Blood and Bone Marrow at a given evaluation time	
Response category	Definition #
Complete remission (CR)	No circulating blasts or extramedullary disease (such as lymphadenopathy, splenomegaly, skin/gum infiltration, testicular mass, CNS or soft tissue involvement) Trilineage hematopoiesis (TLH) and < 5% blasts neutrophils $\geq 1.0 \times 10^9/L$ platelets $\geq 100 \times 10^9/L$ No recurrence for 4 weeks
Complete remission with incomplete blood count recovery (CRI)	Peripheral blood Recovery of platelets but $< 100 \times 10^9/L$ or neutrophils is $< 1.0 \times 10^9/L$ .
Progressive Disease (PD)	Increase of at least 25% in the absolute number of circulating or bone marrow blasts or development of extramedullary disease.
Treatment failure	Treatment failure includes those patients for whom treatment has failed to achieve a CR at the end of treatment
Relapse from CR or CRI	Only in patients with a CR or CRI: Reappearance of blasts in peripheral blood ( $> 1\%$ ) OR $\geq 5\%$ blasts in bone marrow OR (Re-)appearance of extramedullary disease
No response	In case a patient does not achieve CR, CRI, PR or relapse for an individual response assessment.
Unknown	In case the response assessment was not done, the baseline assessment was not done, the assessment was incomplete or was not done within the respective time frame.
#If not defined otherwise, all of the criteria apply.	

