  - b. **Lymphoma:** Patient has at least one measurable nodal lesion ( $\geq 2$  cm) according to International Working Group (IWG) criteria ([Cheson 2007](#)). In case where the patient has no measurable nodal lesions  $\geq 2$  cm in the long axis at screening, then the patient must have at least one measurable extra-nodal lesion ([Appendix C](#))
  - c. **Symptomatic Multiple Myeloma:** by International Myeloma Working Group (IMWG)
    - i. Serum M-component of  $\geq 1$  gm/dL
    - ii. Urine M-component of  $\geq 200$  mg/24 h
    - iii. Patients with plasmacytoma must have a definite increase in the size; a definite increase is defined as a 50% (and at least 1 cm) increase as measured serially by the sum of the products of the cross-diameters of the measurable lesion

d. **Leukemia only:** Relapsed/refractory leukemia for which no standard therapy options are anticipated to result in a durable remission:

- Acute myelogenous leukemia (AML) by World Health Organization (WHO) classification or acute lymphoblastic leukemia (ALL) relapsed or refractory to standard chemotherapy; unsuitable for standard chemotherapy or unwilling to undergo standard chemotherapy. Philadelphia chromosome (Ph) positive ALL eligible if failed prior tyrosine-kinase inhibitor therapy.
- Age  $> 60$  years with AML not candidates for or have refused standard chemotherapy, excluding patients with acute promyelocytic leukemia (APL) or with favorable cytogenetic abnormalities [inv16, t(8;21)].
- For patients with Chronic Myeloid Leukemia (CML) only accelerated and blast phase CML will be allowed.

10. Patient has an Eastern Cooperative Oncology Group (ECOG) performance status  $\leq 1$  ([Appendix K](#)).

11. Patient has a life expectancy of at least 16 weeks.

12. Patients must have adequate bone marrow as described below:

- Absolute Neutrophil Count (ANC)  $\geq 1.5 \times 10^9/L$  (no growth factor within past 14 days) (not applicable for leukemia patients)
- Platelets (PLT)  $\geq 100 \times 10^9/L$  (no platelet transfusion within past 14 days) (not applicable for leukemia patients)
- Hemoglobin (Hgb)  $\geq 9 \text{ g/dL}$  (no blood transfusion within past 14 days) (not applicable for leukemia patients)
- International Normalized Ratio (INR)  $\leq 1.5$

13. All patients must have adequate organ function defined as described below:

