## Appendix F: Criteria for Response assessment in Acute Myeloid Leukemia (based on IWG and Cheson)

Disease assessments will be based on standardized response criteria as defined by the International Working Group (IWG) for AML ([Cheson, et al 2003](#)).

Response classification in AML at a given evaluation time (Cheson 2003)	
Response category	Definition #
Complete remission (CR)	
Bone marrow            < 5% blasts            no blasts with Auer rods
 
Peripheral blood            neutrophils <math>\geq 1.0 \times 10^9/L</math>            platelets <math>\geq 100 \times 10^9/L</math>  <math>\leq 1\%</math> blasts            No evidence of extramedullary disease (such as CNS or soft tissue involvement). Transfusion independent (see Section 7.2.1.4.5).
 
In case all criteria for CR apply and the patient receives platelet and/or neutrophil transfusions, the patient will be assessed as CRI.

Complete remission with incomplete blood count recovery (CRI)	
Bone marrow            < 5% blasts            no blasts with Auer rods
 
Peripheral blood            neutrophils <math>< 1.0 \times 10^9/L</math> and/or platelets <math>< 100 \times 10^9/L</math>  <math>\leq 1\%</math> blasts            No evidence of extramedullary disease (such as CNS or soft tissue involvement). Transfusion-independent (see Section 7.2.1.4.5). Exception: Platelet and neutrophil transfusions are allowed.

Partial Remission (PR)	
Bone marrow            50% or greater decrease (absolute range 5-25% blasts)            < 5% of blasts contain Auer rods
 
Peripheral blood            neutrophils <math>< 1.0 \times 10^9/L</math> and/or platelets <math>< 100 \times 10^9/L</math>            No evidence of extramedullary disease (such as CNS or soft tissue involvement).

Treatment failure	Treatment failure includes those patients for whom treatment has failed to achieve PR, CRI or CR throughout the treatment.
Relapse from CR or CRI *	Only in patients with a CR or CRI: Reappearance of blasts in peripheral blood ( $> 1\%$ ) OR $\geq 5\%$ blasts in bone marrow OR (Re-)appearance of extramedullary disease
No response	In case a patient does not achieve CR, CRI, PR or relapse for an individual response assessment.

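### The ALL row for remission with incomplete count recovery (Appendix H) states no blast or extramedullary criterion, so a neutropenic patient with persistent blasts meets its printed wording

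*Protocol*

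**What the plan says.** Protocol Appendix H classifies response in ALL. Its CRi row contains one statement, on peripheral blood, which opens with "Recovery of platelets but" and reads in full: "Recovery of platelets but $< 100 \times 10^9/L$ or neutrophils is $< 1.0 \times 10^9/L". The CR row above it also requires "No circulating blasts or extramedullary disease" and "Trilineage hematopoiesis (TLH) and < 5% blasts", together with both count thresholds and four weeks without recurrence. The table's footnote reads "If not defined otherwise, all of the criteria apply". The no-response row reads "In case a patient does not achieve CR, CRI, PR or relapse for an individual response assessment", which places CRi among the outcomes that are not a failure to respond.

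The relapse row covers patients in CR or CRi. It has three alternatives: blasts above 1% reappearing in blood, at least 5% marrow blasts, or extramedullary disease.

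Section 5.2 no. 9d admits relapsed or refractory ALL. No. 12 sets neutrophil and platelet minima and waives them for leukemia; the platelet line ends "no platelet transfusion within past 14 days) (not applicable for leukemia patients". No. 14 caps peripheral blasts at below 50,000/mm3.

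Section 7.2.1.4 allows a response status only when marrow and blood are no more than 5 days apart. Section 7.2.1.4.2 schedules marrow at screening, to confirm CR, or when clinically indicated. SAP 4.2 takes hematological responses from the protocol appendices. SAP 4.1 defines clinical benefit as CR, PR or SD for at least 16 weeks.

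**The concern.** A remission category should require that the leukemia has cleared and should relax only the blood-count part. As printed, the ALL row keeps the count part and drops the rest. Low neutrophils are common to active marrow disease, to drug-induced myelosuppression and to a cleared marrow that is slow to recover, so the neutrophil limb cannot tell them apart.

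Two things follow if the row is applied literally. A patient with unchanged disease can be recorded in a remission category. The same patient can then be recorded as relapsing from a remission that never occurred, and relapse is an event for PFS and ends the duration of response (SAP 4.3 and 4.4).

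The ALL table defines neither PR nor SD, so CR and CRi are its only favorable categories. How CRi is scored therefore matters for any ALL result.

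**Working it through.** **1. The rows side by side**

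| Criterion | ALL CR (App. H) | ALL CRi (App. H) | AML CRi (App. F) |
|---|---|---|---|
| Marrow blasts | < 5% | not stated | < 5%, no Auer rods |
| Circulating blasts | none | not stated | at most 1% |
| Extramedullary disease | none | not stated | none |
| Neutrophils (x 10^9/L) | at least 1.0 | < 1.0 (one alternative) | < 1.0 and/or |
| Platelets (x 10^9/L) | at least 100 | recovered but < 100 (other alternative) | < 100 |
| Four weeks without recurrence | yes | not stated | not stated |

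The AML table carries the same footnote as the ALL table, yet its CRi row writes out its own blast and extramedullary criteria. The footnote joins the criteria within a row; it is not the device that carries CR criteria into CRi.

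**2. An unchanged patient (assumed values)**

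Take 60% marrow blasts, 20,000 blood blasts/mm3, neutrophils 0.4 and platelets 40 x 10^9/L, all the same at a later assessment with a paired marrow.

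- Entry: the count minima are waived and 20,000 < 50,000, so the count criteria do not exclude the patient.
- CR: not met (blasts present).
- CRi, neutrophil limb: 0.4 < 1.0, met as written.
- CRi, platelet limb: not met, because platelets have not recovered.
- Progression (blast increase of at least 25%): not met, increase 0%.
- Relapse from CR or CRi: 60% is at least 5%, so the marrow limb is met at the same assessment.

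With neutrophils at or above 1.0 and the same platelets, neither CRi limb is met, so the result turns on neutropenia. If the CR blast and extramedullary criteria carry over, the patient falls to no response.

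**3. How often the neutrophil limb could be met with no effect**

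The documents give no ALL entry counts, so every input here is an assumption: log-normal neutrophils with entry median m, between-patient SD 0.8 and within-patient SD w of 0.25 or 0.4 on the log scale, and two visits. With b the patient's deviation and f its normal density (mean 0, SD 0.8), the chance of a value below 1.0 at either visit is

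P = 1 - integral of f(b) x [1 - Phi((ln 1.0 - ln m - b)/w)]^2 db.

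| m (x 10^9/L) | w = 0.25 | w = 0.4 |
|---|---|---|
| 1.2 | 48% | 52% |
| 2.0 | 25% | 29% |
| 3.0 | 12% | 16% |

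These are shares meeting the printed limb, not shares that would be recorded as CRi. They assume that each low count has a marrow within 5 days and that the row is read literally.

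**4. Effect on a small cohort**

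Appendix R sets the size at which another tumor type may enter the Bayesian analysis at 4 patients in its section 1 and at 3 in section 1.2. One misclassified patient would move the observed rate by 1/4 = 25 or 1/3 = 33 percentage points, if CRi were counted.

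**The case against.** The best defence is that blast clearance was plainly intended. The category is named as a complete remission, and the relapse row speaks of blasts reappearing. The table covers blood and bone marrow, and Section 7.2.1.4 does not allow a response status without a marrow sample close to the blood sample. An investigator who recorded CRi with frank blasts would have to ignore the category's name. All of this stands as evidence of intent. It does not supply the missing criterion: the pairing rule requires a marrow sample but sets no blast limit for CRi.

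Four stronger readings are tempting, and the documents do not support them.

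- A reader might infer that low counts of either kind suffice. Under the same assumptions, with platelet medians of 60, 100 and 150, that would give 45% to 91%. The platelet limb requires recovery, so those figures do not describe the printed rule.
- A reader might infer that a patient is in remission on Day 1. The protocol's Glossary makes pre-dose Cycle 1 Day 1 the baseline, so the question arises only afterwards.
- A reader might infer that leukemia patients may enter with any counts. The neutrophil, platelet and hemoglobin minima are waived, but the blast cap remains.
- A reader might take the 47.7% neutropenia in the phase I study (Section 1.2.1.2.1) as the rate of drug-induced CRi. That figure covers all grades, in solid tumors or lymphoma. Neutropenia there was most often Grade 2, which Table 6-3 puts at or above 1.0.

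The effect on ORR and CBR is also conditional. SAP 4.1 does not map CRi to CR, PR or SD, and the ALL treatment-failure row names only CR.

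**Conclusion.** The omission is real and should be corrected. The ALL CRi row leaves out three criteria that the ALL CR row and the AML CRi row both state. As printed, a neutropenic patient with persistent blasts meets it at a post-baseline assessment and, with at least 5% marrow blasts, meets the relapse row too.

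This is a drafting gap that invites misclassification. It is not evidence that the sponsor meant active ALL to count as remission. The 12% to 52% range is illustrative and rests wholly on assumed entry medians and variances.

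The reach is small. ALL is not among the tumor types expected in Section 5.1 or the example cohorts in Appendix R. A hematological type with fewer than 4 patients is only listed (SAP 2.2, 4.1 and 4.2), and a cohort under 3 patients is left out of the Bayesian analyses (SAP 8.1.2). The documents do not give the number of ALL patients enrolled. Any effect on ORR or CBR also depends on how CRi is scored, which the SAP leaves open.

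**What to change.** 1. In Appendix H, reconcile the CRi row with the ALL CR row and the AML CRi row. CRi should mean that every ALL CR criterion holds (no circulating blasts, no extramedullary disease, marrow blasts below 5%, four weeks without recurrence) except the platelet or the neutrophil threshold.
2. In SAP 4.1 and 4.2, state whether CRi counts as CR for ORR and CBR.
3. For consistency, make the marrow wording in Section 7.2.1.4.2 and Table 7-1 cover CRi as well as CR.

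The cost is one table cell and a few lines. The 5-day rule already requires a marrow sample for any response status, so the third change only makes the schedule match that rule, and it affects only patients being considered for CRi. Any ALL patient already recorded as CRi should be checked against the corrected row before the response data are reported.

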## Appendix I: Criteria for Response assessment in Chronic Myelogenous Leukemia (based on NCCN Guidelines Version 4. 2013)

Response classification in CML for hematologic, cytogenetic, and molecular evaluation at a given evaluation time	
Response category	Definition #
Complete hematologic response (CR) 	Complete normalization of peripheral blood counts with leukocyte count < 10 x 10  /L platelets < 450 x 10  /L No immature cells such as myelocytes, promyelocytes, or blasts in peripheral blood No signs and symptoms of disease with disappearance of splenomegaly
Cytogenetic response 	Complete No Ph-positive metaphases Partial 1% - 35% Ph-positive metaphases Major 0% - 35% Ph-positive metaphases (complete + partial) Minor > 35% Ph-positive metaphases
Molecular response 	Complete No detectable BCR-ABL mRNA by QPCR using an assay with a sensitivity of at least 4.5 logs below standardized baseline. Major ≥ 3 log reduction in international scale of BCR-ABL mRNA
Treatment failure	Treatment failure includes those patients for whom treatment has failed to achieve a complete hematologic response (CR) throughout treatment.
No response	In case a patient does not achieve CR, PR or relapse for an individual response assessment.
Unknown	In case the response assessment was not done, the baseline assessment was not done, the assessment was incomplete or was not done within the respective time frame

# If not defined otherwise, all of the criteria apply.

1. Federl S et al: Chronic myelogenous leukemia: Biology and therapy. Ann Intern Med 1999; 131:207-219.
2. A minimum of 20 metaphases should be examined.
3. O'Brien SG, et al: Imatinib compared with interferon and low-dose cytarabine for newly diagnosed chronic-phase chronic myeloid leukemia. N Engl J Med 2003;348:994-1004.
4. Hughes TP, et al: Frequency of major molecular responses to imatinib or interferon alfa plus cytarabine in newly diagnoses chronic myeloid leukemia. N Engl J Med 2003;349:1423-1432
5. Hughes T, et al: Monitoring CML patients responding to treatment with tyrosine kinase inhibitors; review and recommendations for harmonizing current methodology for detecting BCR-ABL transcripts and kinase domain mutations and for expressing results. Blood 2006;108:28-37

## Appendix J: Criteria for Response assessment in Chronic Lymphocytic Leukemia (based on modified IWG guidelines)

Disease assessments will be based on standardized response criteria as defined by the modified IWG guidelines for CLL. Response in CLL must meet the criteria in both Group A and Group B. Group A criteria defines tumor load. Group B criteria define the function of the hematopoietic system (or marrow).

### Response Definition for Chronic Lymphocytic Leukemia

#### Group A Response for Tumor Burden

Response	Nodal Masses	Organomegaly	Bone Marrow
CR	None > 1.5 cm	No splenomegaly No hepatomegaly	Normocellular >30% Lymph. No B lymphoid nodules
CRi	None > 1.5 cm	No splenomegaly No hepatomegaly	Hypocellular marrow
PR	Decrease ≥50%	Spleen/Liver decrease ≥50	50% reduction in marrow infiltrate, or B-lymphoid nodules

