## Appendix E: Rai Staging Systema

Stage	Area of involvement	Risk Status
0	Lymphocytosis, lymphocytes in blood $>15 \times 10^9/L$ and $>40\%$ lymphocytes in bone marrow	Low
I	Stage 0 with enlarged node(s)	
II	Stage 0-1 with splenomegaly, hepatomegaly, or both	Intermediate
III b	Stage 0-II with hemoglobin $<11.0 \text{ g/dL}$ or hematocrit $<33\%$	Intermediate
IV b	Stage 0-III with platelets $<100 \times 10^9/L$	High
		High

a Research originally published in Blood. Rai KR,et al. Clinical staging of chronic lymphocytic leukemia. Blood 1975;46(2):219-234. (c) The American Society of Hematology

b Immune-mediated cytopenias are not the basis for these stage definitions.

[figure not shown]
[figure not shown]

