#### Group B Response for hematopoietic system^2

Response	Platelet count	Hemoglobin	Neutrophils
CR	>100 x 10  /L	>11 g/dL	>1.5 x 10  /L
CRi	If meets criteria from Group A but does not meet criteria from Group B		
PR	>100 x 10  /L or increase ≥50% over baseline	>11 g/dL or increase ≥50% over baseline	>1.5 x 10  /L or >50% improvement over baseline
SD	Failure to attain CR/CRi/PR or PD		
Relapsed disease or PD	Appearance of any new lesions; at least one of the above criteria. Isolated progressive lymphocytosis in the setting of reduced lymph node size or organomegaly or improvement in hemoglobin/platelets will not be considered progressive disease		

 Hallek M, et al. Guidelines for the diagnosis and treatment of chronic lymphocytic leukemia updating the National Cancer Institute-Working Group 1996 Guidelines. Blood 2008; 111:5446-5456

 All values are without transfusion or hematopoietic growth factors

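### Appendix J makes marrow lymphocytes in CLL complete response a floor (above 30%) where the protocol's other text implies a ceiling, so CR and PR are mis-assigned in a narrow set of patients

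*Protocol*

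**What the plan says.** Protocol 7.2.1.4 assigns CLL response to Appendix J. The appendix states that "Response in CLL must meet the criteria in both Group A and Group B" and that "Group A criteria defines tumor load", while Group B covers blood counts.

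The marrow column of Group A has three entries:
- CR: "Normocellular >30% Lymph. No B lymphoid nodules"
- CRi: "Hypocellular marrow"
- PR: "50% reduction in marrow infiltrate, or B-lymphoid nodules"

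Group B adds a second route to CRi: "If meets criteria from Group A but does not meet criteria from Group B".

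Appendix E (Rai staging) defines stage 0 partly by more than 40% "lymphocytes in bone marrow", and each higher stage builds on a lower one.

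Protocol 7.2.1.4 limits the CLL marrow biopsy to confirming a complete response in patients whose marrow was involved before treatment.

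SAP 4.2 has no CLL criteria of its own. It refers to the protocol appendices, reports each hematological tumor type separately, and gives only a listing when a type has fewer than 4 patients.

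**The concern.** If Group A measures tumor load, a complete response should set an upper limit on marrow lymphocytes. The printed row sets a lower one. A marrow that meets the Rai stage 0 level already passes the lymphocyte part of the CR entry before treatment, and a marrow that clears fails it. The PR row asks for a halving of the infiltrate, but the CR row, which should be stricter, asks for no reduction.

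The biopsy is there to confirm CR, so the reversed sign acts at the step meant to exclude false complete responses. At stake are the CR and PR counts for CLL in SAP 4.2 and, under one reading of the table, the overall response rate (the key secondary endpoint, Protocol 10.5.1) and the start of a duration of response (SAP 4.3).

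**Working it through.** The plan gives no computed figure to reproduce. The check applies the printed rule to example marrow values and compares the result with a ceiling.

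**Inputs**
- CR marrow limit, more than 30% lymphocytes: Appendix J, Group A.
- PR marrow limit, 50% reduction of infiltrate: same table.
- Rai stage 0, more than 40% marrow lymphocytes: Appendix E.
- The marrow percentages below are illustrative, because the documents contain no patient data.

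**Assumptions**
- The marrow was involved before treatment and is now normocellular and free of nodules.
- Nodes, organs and Group B counts are at CR level and also satisfy the other PR columns. No progression criterion is met.
- Infiltrate is measured as percent lymphocytes.

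**Formula.** Relative fall = (baseline − post) / baseline.
- 70% to 45%: 25/70 = 35.7%
- 60% to 60%: 0/60 = 0%
- 70% to 10%: 60/70 = 85.7%
- 45% to 25%: 20/45 = 44.4%

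Appendix J does not say whether a PR must satisfy the marrow column, so both readings are shown.

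| Baseline to post | Fall | As printed, PR marrow column required | As printed, not required | Ceiling, required | Ceiling, not required |
|---|---|---|---|---|---|
| 70% to 45% | 35.7% | CR | CR | SD | PR |
| 60% to 60% | 0% | CR | CR | SD | PR |
| 70% to 10% | 85.7% | PR | PR | CR | CR |
| 45% to 25% | 44.4% | SD | PR | CR | CR |

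The last two rows are not CRi as printed. The marrow is not hypocellular, and the Group B route needs Group A met with counts failing, whereas here the counts are met.

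**Reading across the table**
- In all four rows the category differs between the printed rule and the ceiling, under either reading. The CR count is therefore wrong whichever reading applies.
- If the PR marrow column is required, the printed rule adds a responder in rows 1 and 2 and removes one in row 4. Row 3 stays a responder.
- If it is not required, every row is a responder under both rules, and the overall response rate does not move.
- A responder can be lost only when the post value is at or below 30% but above half of baseline, so baseline must be below 60%.

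**How often the printed CR row accepts what the PR marrow rule would not.** Take whole-percent values, baseline 41 to 100 and post from 0 to baseline.
- All pairs: sum of (b + 1) = 60 × 71.5 = 4,290.
- Pairs passing the printed CR limit (post 31 or more): sum of (b − 30) = 60 × 40.5 = 2,430.
- Of those, 2,030 fell by less than 50%.

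These are counts of arithmetic cases, not patient frequencies.

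**Effect on the reported rate, if the PR marrow column is required.** At 4 patients, the smallest CLL group for which the SAP gives a table, one misclassified patient moves the overall response rate by 100/4 = 25 percentage points.

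**The case against.** The strongest reply accepts that the sign is odd and disputes the consequences. Most of it stands.

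- A reader might infer that every CLL patient with normal nodes and counts is misclassified. The documents do not support this. Marrow is taken only to confirm CR after prior involvement, a hypocellular marrow goes to the CRi row, and nodules point to the PR row. None of these depends on the sign.
- A reader might infer that every CLL patient already meets the marrow part of CR at entry. That also fails. The same cell requires normal cellularity and no nodules, and the Rai threshold is a staging definition. The eligibility criteria set no marrow threshold for CLL.
- A reader might infer that each persisting infiltrate adds a false responder. That needs the PR marrow column to be mandatory. Since marrow is taken only to confirm CR, PR would ordinarily be called without it, and a baseline percentage may not be on record. For lymphoma, Appendix C 4.1.8 treats a patient in CR by other criteria with persisting marrow involvement as a partial responder. That rule does not formally govern CLL, but it shows PR is a plausible fallback. With it, the overall response rate and the start of response are unchanged.
- Clinical benefit is unlikely to move. SAP 4.1 counts CR, PR and SD alike under its 16-week rule.
- CLL is not one of the eight example cohorts in Appendix R, and no CLL count is given. Any percentage-point effect therefore rests on an assumed group size.
- Extracted text can alter a symbol, and the same table prints a spleen and liver limit of 50 without a percent sign. This justifies checking the PDF. It does not explain the sign away: nothing shows a misreading, and taking 30% as cellularity would leave the word for lymphocytes without a function.

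The objection does not reach the contradiction itself. No other section corrects the CR entry, and the SAP relies on it.

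**Conclusion.** The point holds in limited form. The CR marrow entry for CLL runs in the wrong direction when read against the rest of Appendix J and against Appendix E, and the SAP uses it as an operative threshold. The conclusion rests on this internal contradiction and needs no outside source.

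The reach is narrow: prior marrow involvement, a normocellular and nodule-free marrow, and everything else at CR level. In that group the certain consequence is a wrong split between CR and PR, in the SAP 4.2 table or in a listing if there are fewer than 4 CLL patients. Overall response rate and duration of response are affected only if a PR must meet the marrow column, and then in either direction. No numerical effect on the trial can be stated, because the number of CLL patients is unknown. The 25-point figure is a conditional illustration, not an estimate.

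**What to change.** 1. Check the sign in the source PDF of Appendix J.
2. If it is as printed, reverse it so that the CR marrow entry is a ceiling: normocellular, less than 30% lymphocytes, no B-lymphoid nodules. The documents establish the direction but not whether exactly 30% qualifies, so confirm the boundary against the criteria Appendix J cites.
3. Reconcile the CR row with the opening text of Appendix J, the PR row and Appendix E. State whether PR in CLL requires the marrow column, and which category applies when only the marrow fails CR.
4. Re-derive the response category of any CLL patient already assessed and update the SAP 4.2 output, and the duration of response if responder status changes.

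The text change is small, but under Protocol 12.1 it needs a written, approved amendment. Enrollment is closed (Amendment 3), so the practical work is re-deriving whatever CLL cases exist. No new data collection follows from the sign change itself.
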